2. LOCATION

Central Clinical School, Alfred Centre, Monash University.

3. PURPOSE OF THE STUDY:

To determine the efficacy of the low FODMAP diet in reducing gastrointestinal symptoms in women with endometriosis experiencing gastrointestinal symptoms.

To determine if changes in gastrointestinal and gynaecological microbiome is associated with gastrointestinal symptoms in patient with endometriosis and whether this is modified by the low FODMAP diet.

4. BACKGROUND:

Endometriosis is a common condition that affects more than 700,000 Australian women, although this number is likely to be far higher owing to delays in diagnosis, misdiagnosis and a lack of research into the domestic burden of the disease¹. It is associated with severe dysmenorrhoea, menorrhagia, (very painful and heavy periods), chronic abdominal pain, and frequently bowel symptoms similar to those typically associated with irritable bowel syndrome (IBS)². The association between IBS and endometriosis is not new, with difficulties distinguishing the two conditions frequently raised as a clinical concern³. Many patients with endometriosis experience abdominal bloating, diarrhoea and/or constipation, common symptoms of IBS, which itself affects up to 15% of the population⁴. When a woman presents with chronic abdominal and/or pelvic symptoms, defining the cause – endometriosis, IBS or both - can be challenging. This dilemma may in part contribute to the average delay of between 6 and 11 years before an eventual diagnosis of endometriosis is made^{5,6}.

Endometriosis may be asymptomatic, resulting in subfertility (up to 37% of individuals affected)⁷, or it can present with chronic, intractable symptoms characterised by debilitating chronic pain; symptom recurrence; compromised fertility; impaired sexual function, and a substantial reduction in quality of life (QOL). It negatively impacts the families and partners of women affected and costs the country an estimated 7.7 billion annually in healthcare costs, absenteeism and reduced economic participation⁸. Gastrointestinal (GI) complaints such as

diarrhoea and constipation are common among women with endometriosis, affecting up to 90% of patients⁹. Psychological co-morbidities are also common. However, there are few evidence-based treatment options (particularly lifestyle therapies) for these. As such, our research will address a gap in knowledge that is of considerable interest to consumers, namely the efficacy of the low FODMAP diet in the management of GI symptoms associated with endometriosis. Despite the lack of evidence, this diet is regularly prescribed by clinicians and used by patients on account of anecdotal reports of efficacy. Our randomised controlled trial (RCT) of the low FODMAP diet in women with endometriosis and gastrointestinal symptoms will provide high-quality evidence that will inform clinical practice and improve patient outcomes.

There are no RCTs looking at the role of diet in endometriosis, and of the few studies that have looked at food, most were animal or epidemiological studies that examined diet as a risk factor for the development of endometriosis¹⁰. Only three interventional studies examined diet as a therapeutic intervention in endometriosis. In one, fish oil contributed no difference in recurrence rates compared to placebo¹¹. In another, a gluten free diet showed a benefit, although this improvement may have been attributable to the concomitant reduction FODMAP intake¹². Finally, our team examined the efficacy of a low FODMAP diet in 116 women with IBS +/- endometriosis¹³. This study is described in greater detail below.

Pioneering research from our team that has been replicated by groups world-over has definitively shown that a low FODMAP diet reduces GI symptoms in the majority of IBS patients. FODMAP is an acronym (Fermentable Oligo- Di- and Mono-saccharides And Polyols) that represents a group of short-chain carbohydrates that are poorly absorbed and rapidly fermented in the intestine. These actions promote water movement into the bowel, gas production, and secondary changes in bowel habit and intestinal distension¹⁴. A FODMAP diet restricts intake of short-chain carbohydrates.

With growing recognition of the overlapping symptoms between endometriosis and IBS; the preponderance of IBS in people with endometriosis (and vice versa); and observations that visceral hypersensitivity (a hallmark feature of IBS) is also present in endometriosis, our team conducted a retrospective, observational study which showed that women with both endometriosis and IBS were more likely to report at least a halving of bowel symptoms after 4 weeks on a low FODMAP diet¹³. While these results were impressive, they were limited by the retrospective design, the lack of laparoscopically confirmed disease and recruitment of patients primarily with IBS symptoms. To improve the diagnosis and treatment of endometriosis, there is also an urgent, unmet need to understand the pathophysiological mechanisms underlying GI symptoms in endometriosis. While GI symptoms may be secondary to extra-genital endometriosis, only 7% of patients have bowel endometrial deposits, suggesting that other pathologies more often predominate¹⁵. However, at present,

aetiological mechanisms remain elusive.

Alteration of the GI microbiota is considered a key aetiopathological factor in the development of IBS, and there is an increasing interest in the role that intestinal and/or vaginal dysbiosis may play in the pathogenesis of endometriosis.

Differences in gut microbiota have been seen with an interventional low FODMAP diet¹⁹(Halmos 2015), in patients with GI symptoms, but what the influence of this diet would be on microbiota in a woman with both endometriosis and GI symptoms remains to be seen. If intestinal dysbiosis is associated with GI symptoms and endometriosis, will changes be seen in microbiota in these women with the application of the low FODMAP diet?

5. HYPOTHESES:

Study 1a; The low FODMAP diet will be efficacious in relieving GI symptoms in women with endometriosis.

Study 1b; Microbiome structure and function will change in response to the low FODMAP diet in women with endometriosis and GI symptoms.

6. PARTICIPANTS:

Thirty-two women aged from 18 and over, are pre-menopausal, with endometriosis and concurrent inadequately controlled GI symptoms will be recruited via advertisements, including at gynaecological consultation rooms such as the Monash Health Department of Obstetrics and Gynaecology, The Mercy Health Service, and via support groups such as Endometriosis Australia and Endo-active.

7. INTERVENTION AND STUDY DESIGN:

The study will be a double-blinded, randomised crossover design. Given symptoms are known to vary across the menstrual cycle, baseline data will be collected for the 7 days preceding the due date of their period (days -7 to 0) unless menstrual cycles are hormonally suppressed. If women are hormonally suppressed, data will be collected for the 7 days prior to randomisation and commencement of the study. Participants will complete the symptom and QOL measures as described below. In addition, a daily food and symptom diary and bowel diary will be completed.

[figure not shown]
A low FODMAP diet and a control diet will be provided to participants according to the study

design. The 2 test diets will be identical in nutritional needs. The low FODMAP diet will limit oligosaccharide, fructose in excess of glucose, and polyol content to less than 0.5 g per sitting based on previously published data²⁰. The control diet will represent a 'typical Australian diet' and mimic the average FODMAP intake of Australians based on a previously validated food frequency questionnaire²¹. To assist with compliance, all food will be prepared by our research chef and dietitian and supplied to the subjects to heat and consume at home. FODMAP containing foods will be masked in the supplied meals to assist with blinding.

Prior to randomisation, following informed signed consent, potential participants will complete the Patient Reported Outcome Measures Information System-Gastrointestinal Symptom Scale (PROMIS-GI) questionnaire, Women's health symptom questionnaire; Endometriosis Health Profile (EHP-30) overall symptom severity Visual Analogue Scale (VAS) Gastrointestinal Quality of Life measure (GIQLI), and the Depression, Anxiety and Stress Scale (DASS – 21) questionnaires. On day 0, eligible participants will be randomised in a 50:50 ratio to a low FODMAP diet or control diet for 28 days (day 0-28). To overcome difficulties with blinding (the low FODMAP diet is well known in Australia) all food will be provided to participants for days 0 – 28 and days 57 – 84. Participants will undergo a washout between days 29 to 56, during which they will consume their habitual diet. Participants will then cross over to the alternate diet, either low FODMAP or control for a further 28 days (day 57 - 84). Participants with hormonally suppressed menstrual cycles can commence the study at any time. Dietary compliance will be assessed using food diaries (proportion of prepared meal consumed and additional food consumed), recorded daily throughout the study. Participants will be given a list of appropriate snacks and drinks that will not interfere with the different diets. Also, throughout the study participants will be instructed to complete a daily bowel habit and symptom diary. On day 28 and day 84 participants will complete the questionnaires listed above again except for the Women's health symptom questionnaire which is for baseline data only. Also on days 28 and 84 participants will collect fresh stool and a vaginal swab which will be immediately frozen for subsequent analysis (see study 1b). Stool and vaginal samples will be collected into Omnigene collection tubes to stabilise microbial DNA (see section 1b below). Detailed instructions on how to collect these samples will be provided.

Analyses of the stool and vaginal microbiota will be undertaken using DNA extracted from these samples by [name] group at the University of Queensland (UQ).

Figure 1: Design of Study 1a and 1b.

8. OUTCOME MEASURES:

Primary outcome: GI symptom severity as compared at baseline and at the end of each dietary intervention. (symptom VAS score)

Secondary outcomes:

- Specific GI symptoms (PROMIS GI)
- Effect of endometriosis symptoms (EHP-30)
- Quality of life (GIQLI)
- Psychological status (DASS 21)
- Stool microbiota dynamics (study 1b)
- Vaginal microbiota dynamics (study 1b)
- Daily bowel and symptom diary

9. INVESTIGATIVE TECHNIQUES:

Questionnaires

- Overall symptom severity VAS (0-100 where 0 = no symptoms and 100 worst possible)
- PROMIS GI questionnaire (NIH, Spiegel et al 2014)

This validated questionnaire is the *Patient Reported Outcome Measures Information System Gastro-Intestinal Symptom Scale* (PROMIS GI) where overall initial symptom scores will be assessed on the 7 days prior to randomisation.

- Endometriosis Health Profile - (EHP-30)

A validated questionnaire that explores how symptoms of endometriosis affect day to day life

- GIQLI

This is a comprehensive questionnaire on overall GI Quality of Life Indicator as validated by....

- DASS 21 (OEI et al 2014)

Psychological status will be measured by this Depression, Anxiety and Stress Scale; a validated assessment of stress levels.

Pathology (study 1b)

- Stool sample

A fresh stool sample will be collected by the participant into an Omnigene collection tube and immediately frozen for subsequent analysis

- Vaginal swab

A clean vaginal swab will be collected by the participant and placed into an Omnigene tube, and frozen as per stool sample.

10. INCLUSION CRITERIA:

- Women with an existing diagnosis of endometriosis with inadequately controlled gastrointestinal symptoms
- Over age 18, regular periods with a cycle between 24 and 30 days, or on hormonal therapy for endometriosis symptoms
- Women need to show inadequate GI symptom control by answering “no” to the screening question “*Over the past week were your bowel and gut symptoms adequately controlled?*”
- Mean overall symptom VAS score of >30mm.

11. EXCLUSION CRITERIA:

- Women with significant food intolerances and food allergies, e.g. nuts; an overly restricted diet, vegan, or a current history of an eating disorder. Significant concurrent health issues such as diabetes, recent laparoscopic surgery in the last 3 months, past bilateral salpingo-oophorectomy, (removal of both ovaries) coeliac disease and/or other gastrointestinal disease such as inflammatory bowel disease (IBD), bowel resection, malnutrition and active major psychological illness.
- An erratic menstrual cycle.
- Women taking antibiotics and/or probiotics for 4 weeks prior to and/or during the proposed study period.
- Women who are pregnant or planning to become pregnant during the study period.
- Insufficient symptom score in VAS of <30mm symptom severity in baseline week.
- Women already on a low FODMAP diet that are not willing to cease using this diet. (At recruitment women will not be told of the involvement of FODMAPs)
- Insufficient English comprehension requiring use of translator
- Women already undertaking a restricted diet (i.e Vegan, Gluten Free)

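### For women with natural cycles, baseline VAS is tied to the premenstrual week, but the end-of-diet VAS is fixed on days 28 and 84, which keep that phase only for a 28-day cycle

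*Protocol*

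**What the plan says.** All references are to the protocol.

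- **Baseline, section 7:** "Given symptoms are known to vary across the menstrual cycle, baseline data will be collected for the 7 days preceding the due date" of the period. The window is labelled days -7 to 0, so day 0 is the due date.
- **Hormonally suppressed women, section 7:** "data will be collected for the 7 days prior to randomisation and commencement of the study", with no link to a cycle.
- **End of diet, section 7:** "On day 28 and day 84 participants will complete the questionnaires listed above again". The overall symptom VAS is one of these questionnaires. The washout (days 29 to 56) and second diet (days 57 to 84) also run by calendar. No due date, window or averaging is attached to day 28 or day 84.
- **Primary outcome, section 8:** the symptom VAS, compared at baseline and at the end of each diet.
- **Eligible cycles, section 10:** "regular periods with a cycle between 24 and 30 days", or hormonal therapy for endometriosis symptoms.
- **Baseline VAS as a weekly value:** "Mean overall symptom VAS score of >30mm" (section 10) and "Insufficient symptom score in VAS of <30mm symptom severity in baseline week" (section 11).
- **Analysis, section 12:** end-points across treatment periods are compared by one-way ANOVA.

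**The concern.** The protocol gives its own reason for controlling cycle phase, applies that control at baseline, and does not carry it to the two assessments that form the primary outcome. A 28-day diet followed by a 28-day washout and a further 28-day diet keeps the phase constant only in a woman whose cycle is exactly 28 days. For other permitted lengths the drift builds up, so day 84 is further out of phase than day 28.

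There is a second mismatch. A weekly mean at baseline is set against what reads as one day's score at the end of each diet, and one day's score carries more day-to-day variation.

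Two comparisons are at stake. Change from baseline could partly reflect a move from the premenstrual week to another part of the cycle. The comparison between diets could lose precision, which matters with about 24 completers. If VAS scores are collected only on days 28 and 84, no later analysis plan can recover a weekly value.

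**Working it through.** The protocol states no figure for this point, so the check is calendar arithmetic.

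**Inputs.** Day 0 = due date and baseline window -7 to 0 (section 7); assessments on days 28 and 84 (section 7); whole-day cycle lengths L = 24 to 30 (section 10). Cycles are taken as perfectly regular, so due dates fall on L, 2L, 3L and so on.

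**Step 1: distance from the nearest due date.** Offset = study day minus nearest multiple of L. Example, L = 25: 28 - 25 = +3 and 84 - 75 = +9. At L = 24, day 84 lies midway between due dates 72 and 96 and is shown as 84 - 72 = +12.

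| Cycle length | Day 28 | Day 84 | Difference (day 84 minus day 28) | In -7 to 0 window? |
|---|---|---|---|---|
| 24 | +4 | +12 | +8 | neither |
| 25 | +3 | +9 | +6 | neither |
| 26 | +2 | +6 | +4 | neither |
| 27 | +1 | +3 | +2 | neither |
| 28 | 0 | 0 | 0 | both |
| 29 | -1 | -3 | -2 | both |
| 30 | -2 | -6 | -4 | both |

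Both readings miss the window for 4 of 7 lengths. They are in phase with each other for 1 of 7.

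**Step 2: would a weekly mean on the same calendar days be enough?** Count how many of the 7 days before each assessment (days 21 to 27 and 77 to 83) lie 7 to 1 days before a due date.

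| Cycle length | 24 | 25 | 26 | 27 | 28 | 29 | 30 |
|---|---|---|---|---|---|---|---|
| Before day 28 | 3 | 4 | 5 | 6 | 7 | 6 | 5 |
| Before day 84 | 0 | 0 | 1 | 4 | 7 | 4 | 1 |

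A weekly mean removes the averaging mismatch but not the phase mismatch. Cycle position must also be recorded and handled in the analysis.

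**Step 3: would restarting the second diet on a due date solve it?** For lengths 24, 25, 26 and 27 the nearest due dates to day 57 are days 48, 50, 52 and 54. A washout running from day 29 to the day before would last 19, 21, 23 and 25 days instead of 28. Waiting for the next due date moves the start to day 72, 75, 78 or 81. This is a material change to the schedule.

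**The case against.** **Scope.** Women on hormonal therapy are eligible, and those who are suppressed have no cycle-anchored baseline. The phase argument does not reach them, and their share is not given. For 28 to 30 days both readings stay inside the window. At day 28 the offset is never more than 4 days; offsets of 6 days or more after the due date arise only at day 84 with cycles of 24 to 26 days. All of this stands. A reader might infer that most women are affected, but 4 of 7 counts lengths, and no distribution of cycle lengths is given.

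**Bias between diets.** A reader might infer that the phase shift could imitate a diet effect. The documents do not support that. Diet order is randomised 50:50, so the day 28 / day 84 difference is spread over both diets and acts as noise and a period effect. What remains is that a one-way ANOVA models neither.

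**Single reading.** The protocol gives no recall period for the VAS, and the screening question and PROMIS GI both refer to a week. Section 7 also lists the pre-randomisation VAS as one questionnaire, so the weekly nature of baseline comes from sections 10 and 11. The design figure is not available. One score on one day is therefore the plain reading, but not a certain one.

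**Power.** It is tempting to quote a loss. Suppose 19 mm (section 12) is the SD of the within-woman difference, n = 24, and the true difference is 11.35 mm, which gives 80% power. Adding an assumed phase SD s per assessment gives SD = √(19² + 2s²): 20.3 mm and 75% power at s = 5, 23.7 mm and 61% at s = 10. But the protocol gives neither 11.35 mm nor any phase SD, and the 19 mm may already contain such variation. Gains claimed for averaging are no firmer. With an assumed stable SD of 8 mm and daily SDs of 15 or 20 mm, a single-day paired SD would be √(2(8² + 15²)) = 24.0 mm or √(2(8² + 20²)) = 30.5 mm, both above 19 mm. These figures are illustrations only and carry no weight here.

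**Conclusion.** The point holds in a limited form. For women who are not hormonally suppressed, section 7 does not carry its own cycle anchor to the primary end-of-diet assessments. Both readings fall outside the baseline window for 4 of 7 permitted cycle lengths, and the two diet readings are out of phase with each other for 6 of 7, by 2 to 8 days. This rests on regular whole-day cycles with day 0 as the due date.

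Change from baseline is confounded with cycle phase in these women. The diet comparison remains protected from systematic bias by randomisation but loses precision by an amount the documents do not allow anyone to estimate. The mismatch between a weekly baseline and a single end-of-diet score is likely on the wording, but depends on the unstated recall period. The data collection should be settled before recruitment, since daily scores and bleeding dates cannot be reconstructed afterwards.

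**What to change.** 1. Add the 0-100 VAS to the daily diary. The protocol does not say that the diary holds it now.
2. Define the primary value for each diet as the mean daily VAS over its last 7 days, matching the weekly baseline.
3. Record the first day of each bleed.
4. Compare diet with diet in a within-woman model, such as a mixed model, with terms for diet, period and days from the nearest bleed onset. Give suppressed women zero or a separate level for the cycle term.
5. Add a sensitivity analysis restricted to suppressed women and to women whose end-of-diet weeks are phase-matched.
6. Reconcile the statements in section 7 on whether the cycle anchor is meant to apply to the second period.

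This proposal leaves the diet and washout schedule as written. The cost is one diary line a day, plus one or two extra model terms with about 24 completers. The weekly mean alone does not restore phase matching, so items 3 to 5 are needed with it.

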12. SAMPLE SIZE CALCULATION AND STATISTICAL ANALYSES

Study 1a and 1b: Data analysis and interpretation: A sample size of 24 will be sufficient to detect a change in overall gastrointestinal symptoms. This number was based on data from studies performed in our department in patients with IBS that produced a standard deviation in overall symptom response of 19mm. Assuming a drop-out rate of ~30% a total of 32 will need to be recruited. Comparisons of measured end-points across treatment periods will be assessed by one-way analysis of variance (ANOVA). Bioinformatics on the microbial results will be conducted at UQ by [name] team. The threshold for statistical significance will be set to $p < 0.05$ for all the analyses and corrections for multiple testing by false discovery rate (FDR) with values < 0.05 also considered to be statistically significant. Bonferroni corrections will also be applied to produce adjusted p-values as needed.

13. ETHICAL AND SAFETY RECOMMENDATIONS:

Given the nature of the conditions being examined, and required samples collected it is possible that participants will feel embarrassed discussing their symptoms. Consequently, all interviews will be conducted by a medical professional with detailed knowledge of both endometriosis and gastrointestinal disorders in a private, non-threatening environment.

The diet supplied representing the typical Australian diet may cause GI symptoms, similar or the same as they have been experiencing.

14. REFERENCES:

1. Simoens S, et al. The burden of endometriosis: costs and quality of life of women with endometriosis and treated in referral centres. *Hum Reprod* 2012;27:1292
2. Meurs-Szjoda MM, et al. Irritable bowel syndrome and chronic constipation in patients with endometriosis. *Colorectal Dis* 2011; 13:67
3. Seaman HE et al. Endometriosis and its coexistence with irritable bowel syndrome and pelvic inflammatory disease: findings from a national case-control study – Part 2. *BJOG* 2008; 115:1392.
6. Perry R. Endometriosis: a gynaecological and colorectal disease. *NZMJ.* 2005;118(1217):U1535-U

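### Recruiting 32 women with about 30% dropout leaves about 22 completers, not the 24 that section 12 calls sufficient; the effect is small and restating the figures corrects it

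*Protocol*

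**What the plan says.** Section 12 of the protocol makes three linked statements:

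- The number needed: "A sample size of 24 will be sufficient to detect a change in overall gastrointestinal symptoms".
- The variability behind it, from earlier work of the department in patients with IBS: "a standard deviation in overall symptom response of 19mm".
- The allowance for losses: "Assuming a drop-out rate of ~30% a total of 32 will need to be recruited".

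Section 6 repeats the recruitment figure: "Thirty-two women aged from 18 and over, are pre-menopausal". On design, section 7 says: "The study will be a double-blinded, randomised crossover design". Allocation to the first diet is 50:50, and the questionnaires are repeated on days 28 and 84, at the end of each diet period. The protocol describes no replacement of women who drop out and no other allowance for loss. Section 12 gives neither a target difference nor a power for the 24.

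**The concern.** A number to recruit should be the number needed at the end divided by the proportion expected to stay. Here 24 is raised to 32 for dropout, so 24 must be the number needed after dropout. The increase from 24 to 32 is too small for a 30% loss.

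In a two-period crossover, a woman lost before day 84 gives no within-woman comparison of the two diets, so completers are what count for the main comparison. If the dropout assumption is right, the trial should expect to finish below the number that its own justification relies on. A reader who takes section 12 at face value would credit the trial with slightly more precision than its inputs imply.

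**Working it through.** **Inputs (protocol).** Needed after dropout: n = 24 (section 12). Dropout: d = 0.30 (section 12). Recruited: N = 32 (sections 6 and 12). SD: 19 mm (section 12).

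**1. Where 32 may come from.** Adding 30% to 24 gives 24 × 1.30 = 31.2, rounded up to 32. This reproduces the stated figure. The protocol does not show its working, so this origin is an inference; the steps below do not depend on it.

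**2. Completers expected from 32.** N × (1 − d) = 32 × 0.70 = 22.4, so about 22. The shortfall is 24 − 22.4 = 1.6 women.

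**3. Recruits needed for 24 completers.** n / (1 − d) = 24 / 0.70 = 34.3, so 35. Equal sequences under 50:50 allocation would need an even number, so 36.

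**4. Highest dropout that 32 covers.** 1 − 24/32 = 0.25, that is 25%.

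**5. Does the approximation sign before 30% rescue the figure?** Applying n / (1 − d) and rounding up:

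| Dropout | Completers from 32 | Recruits needed for 24 |
|---|---|---|
| 25% | 24.0 | 32 |
| 26% | 23.7 | 33 |
| 28% | 23.0 | 34 |
| 30% | 22.4 | 35 |

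It does not. Every rate above 25% leaves fewer than 24.

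**6. Chance of reaching 24.** Assume that each woman completes independently with probability 0.70. The binomial probability of at least 24 completers is then about 34% with 32 recruited and about 65% with 35.

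**7. Effect on precision (illustration only).** The standard error is proportional to 1/√n, so going from 24 to 22 raises it by √(24/22) = 1.044, about 4%, whatever the SD.

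Power needs assumptions that the protocol does not give: a paired t-test, two-sided 5%, and 19 mm read as the SD of the within-woman difference. The noncentral t distribution then gives:

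| Power assumed for 24 | Detectable with 24 | Detectable with 22 | Power of 22 at the difference for 24 |
|---|---|---|---|
| 80% | 11.3 mm | 11.9 mm | 76% |
| 90% | 13.1 mm | 13.8 mm | 87% |

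The millimetre figures scale with the SD. If 19 mm is instead the SD of a single score, the SD of the difference is 19 × √(2(1 − ρ)), where ρ is the within-woman correlation:

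- ρ = 0.5: 19.0 mm, as in the table.
- ρ = 0.3: 22.5 mm, and the 80% figures become 13.4 and 14.1 mm.
- ρ = 0.7: 14.7 mm, and they become 8.8 and 9.2 mm.

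The falls from 80% to 76% and from 90% to 87% do not depend on the SD.

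**The case against.** **The dropout rate is only approximate, and the shortfall is under two women.** The second half stands and limits the weight of the point: the change is about half a millimetre on a 0–100 scale and three to four points of power. The first half does not stand, because no rate above 25% is compatible with 32 recruits and 24 completers. Reading about 30% as 25% replaces the stated assumption with another.

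**Nothing shows that 22 is too few.** This stands. A reader might infer that the trial is underpowered. The protocol does not support that: 24 is tied to no target difference or power, so it cannot be treated as a verified threshold that 22 fails. What is shown is that the stated figures disagree.

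**The power figures rest on assumptions.** This also stands. The meaning of the 19 mm is not stated, 80% and 90% are conventional levels chosen for the illustration, and section 12 names a one-way ANOVA, not a paired t-test. The figures show scale and should not be written into the protocol as the sponsor's own.

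**Women who leave after day 28 still contribute first-period data.** True, but they add nothing to the within-woman comparison. It also does not reconcile the sentence, which itself inflates 24 to allow for losses.

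**Conclusion.** Section 12 is wrong as written, with a small effect. Its three figures cannot all hold: 32 recruits at 30% dropout give about 22 completers, 24 completers at 30% need 35 recruits (36 for equal sequences), and 32 recruits give 24 completers only at 25% dropout or less. This part rests on the protocol's own numbers and on dropouts not being replaced, since no replacement is described.

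The consequence is modest: an expected shortfall of 1.6 women and a standard error about 4% larger with 22 than with 24. Under the illustrative paired analysis, power falls by three to four points.

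Two further inferences are tempting and unsupported. One is that more women must be enrolled; the inconsistency can be removed without enrolling anyone. The other is that 25% is the true dropout assumption; it is merely the rate at which the arithmetic closes, and the protocol offers nothing in its favour.

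**What to change.** Keep 32 in sections 6 and 12, keep the 30% dropout, and restate in section 12 that about 22 completers are expected. Recompute the detectable difference and power for 22 from the sponsor's own target difference and SD, saying what the 19 mm measures; the illustrative values above should not be used in their place.

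Two alternatives would also be consistent:

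- State 25% dropout with 32 recruited and 24 completers, but only if the sponsor can justify that rate, for example from completion in its earlier feeding studies.
- If 24 completers at 30% dropout is a firm requirement, raise recruitment to 35 (36 for equal sequences) in both section 6 and section 12. This is the only option that needs more participants: three or four more women.

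The preferred change costs a sentence or two in section 12 and one recalculation. Design, recruitment target and analysis are unchanged. Its downside is that the stated number of completers becomes slightly less favourable.

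### The protocol names a one-way ANOVA for a crossover trial, so the stated test ignores that each woman supplies values on both diets

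*Protocol*

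**What the plan says.** - **Design (section 7).** "The study will be a double-blinded, randomised crossover design". Women start with one diet: "eligible participants will be randomised in a 50:50 ratio to a low FODMAP diet or control diet for 28 days (day 0-28". After a washout on their habitual diet, "Participants will then cross over to the alternate diet, either low FODMAP or control for a further 28 days (day 57 - 84". Each woman who completes therefore has an end-of-diet value on both diets.
- **Primary outcome (section 8).** "GI symptom severity as compared at baseline and at the end of each dietary intervention. (symptom VAS score". A completer has up to three values: baseline, end of low FODMAP and end of control.
- **Analysis (section 12).** "Comparisons of measured end-points across treatment periods will be assessed by one-way analysis of variance (ANOVA". This is the only method named for comparing the end-points.
- **Sample size (section 12).** "A sample size of 24 will be sufficient to detect a change in overall gastrointestinal symptoms". The basis is earlier work in IBS that "produced a standard deviation in overall symptom response of 19mm". No target difference, power or within-woman correlation is given.

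No section mentions a paired comparison, repeated measures, or a participant, period or sequence term.

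**The concern.** A one-way ANOVA assumes that all observations are independent. In this design they come in sets from the same woman, and symptom scores from one woman are expected to resemble each other. That expectation is the usual reason for choosing a crossover: each woman serves as her own control, and stable differences between women drop out of the comparison.

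The named test keeps those differences in the error term. Under positive correlation its standard error is too large, its confidence interval too wide and its true type I error below the nominal 5%. With only 24 evaluable women planned, the practical consequence is that a real benefit of the diet could be missed or reported with needless imprecision.

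This is not a detail left for a statistical analysis plan. The protocol states a method, and that method does not fit its own design.

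**Working it through.** **Inputs from the protocol.** 24 evaluable women; SD 19 mm; significance level 0.05 (section 12). Each woman receives both diets, with 50:50 allocation to the starting diet (section 7).

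**Assumptions, because the protocol is silent.** Two-sided testing; 19 mm is the SD of the VAS on each diet; within-woman correlation r of 0, 0.3, 0.5 or 0.7; complete data; only the two diet values compared, without baseline as a third condition.

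**Step 1. The plan's own figure.** The 24 cannot be reproduced, since no difference or power is stated. Working backwards with 19 mm as the SD of the paired difference and 80% power:
- Normal approximation: 19 × (1.960 + 0.842) / √24 = 10.9 mm.
- Noncentral t: 11.35 mm.

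This difference serves below as the illustrative true effect. It is not a figure from the protocol. If the 24 values per diet are treated as two independent groups with SD 19 mm, the difference detectable with 80% power is 15.7 mm.

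**Step 2. Standard error of the diet difference.**
- One-way: 19 × √(2/24) = 5.48 mm, whatever r is.
- True: 19 × √(2(1 − r)/24).
- Ratio of one-way to true: 1/√(1 − r).

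**Step 3. Interval half-width.** One-way, 46 degrees of freedom: 2.013 × 5.48 = 11.0 mm. Paired, 23 degrees of freedom: 2.069 × true SE.

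**Step 4. Type I error and power at a true 11.35 mm.** One-way results are from simulation (100,000 trials); paired power is from the noncentral t.

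| r | True SE (mm) | SE ratio | Paired half-width (mm) | One-way type I error | One-way power | Paired power |
|---|---|---|---|---|---|---|
| 0 | 5.48 | 1.00 | 11.3 | 5.0% | 53% | 51% |
| 0.3 | 4.59 | 1.20 | 9.5 | 2.0% | 53% | 66% |
| 0.5 | 3.88 | 1.41 | 8.0 | 0.7% | 54% | 80% |
| 0.7 | 3.00 | 1.83 | 6.2 | 0.1% | 55% | 95% |

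One-way power hardly moves with r. What changes is the power that a paired analysis would have had.

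**Step 5. The other reading of 19 mm.** If it is the SD of the within-woman difference, paired power at 11.4 mm is 80% at every r. The per-diet SD becomes 19/√(2(1 − r)), and one-way power is 82%, 70%, 54% and 26% at r = 0, 0.3, 0.5 and 0.7. The direction is the same.

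**Step 6. Does omitting the period term bias the result?** With 12 women per sequence, r = 0.5, no diet effect and a 10 mm period effect, the simulated mean diet difference was 0.0 mm and the one-way test rejected in 0.5% of trials. With balanced sequences the estimate stays unbiased.

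**The case against.** **The authors may have meant a one-way repeated-measures ANOVA.** With three conditions per woman this is a plausible shorthand, and the defect may be little more than a missing qualifier. The possibility stands, but the text does not say it and nothing elsewhere in the protocol implies it. The sentence needs correcting on either reading.

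**The error is conservative.** This also stands. Under positive correlation the stated test does not inflate false positives, so a reader should not infer that it could produce a spurious efficacy claim.

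**The magnitude rests on assumptions.** This is true as well. The correlation, effect size and power are not in the protocol, the meaning of the 19 mm is unclear, and baseline is left out of the calculation. The figures are illustrative.

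Three stronger readings are tempting, and the document supports none of them:
- *That women who stop after the first period are mishandled.* Section 12 says nothing about missing values. A one-way ANOVA on pooled values would keep such a woman; a simple paired test would drop her.
- *That diet cannot be separated from period.* With 50:50 allocation and balanced completers, diet and period are orthogonal, and Step 6 shows no bias. Leaving period out costs precision. Bias would require dropout to unbalance the sequences.
- *That the diet effect cancels because the factor is the treatment period.* This would follow only if calendar period were the ANOVA factor. The hypothesis in section 5 concerns the diet, and section 8 compares values at the end of each dietary intervention, so the natural meaning is the diet conditions. At most the wording is ambiguous.

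**Conclusion.** The stated analysis is wrong as written: a one-way ANOVA does not fit a crossover in which each woman supplies values on both diets, and no within-woman term appears anywhere in the protocol. The consequence is intervals that are too wide and lost power.

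Under the stated assumptions (24 completers, per-diet SD 19 mm, true difference 11.35 mm), power is about 53–55% instead of 66–95% for r between 0.3 and 0.7, and the true type I error is 2.0% down to 0.1%. At r = 0 nothing is lost. That the test and the design do not match is certain from the text. The size of the loss is not, because it depends on a correlation that the protocol does not report and on what the authors meant by the 19 mm.

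**What to change.** Replace the ANOVA sentence in section 12 with a within-participant analysis that:
- makes low FODMAP versus control at the end of each diet the primary contrast, and says that the factor is diet and not calendar period;
- uses, for example, a linear mixed model with diet, period and sequence as fixed effects and participant as a random effect;
- reports the diet difference with a 95% confidence interval;
- keeps comparisons with baseline as secondary, within the same framework.

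The period term protects precision. It also guards against bias if dropout, which section 12 puts at about 30%, leaves the sequences unbalanced. If a repeated-measures ANOVA was intended, the protocol should say so, but that label alone would still not include period or sequence.

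The cost is a short rewrite in section 12, with no additional participants, visits or data. It should be settled before unblinding.
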